## **Study Protocol**

With approval from the Siriraj Institutional Review Board (Number Si 622/2017) and registered ClinicalTrials.gov (NCT03474406), we conducted a prospective observational study of patients 18 years and older who received a new consult for cancer pain at the Siriraj Pain Clinic from January to December 2018. Written informed consent was obtained from all patients. We excluded patients who had difficulties with listening, reading, and writing Thai and those who were unable to interpret the evaluation form/questionnaires.

All patients enrolled in the study received standard care by pain specialists in the clinic. The WHO analgesic guidelines, selective consideration of pain interventions, and nurse-directed analgesic rescue program were implemented. Additionally, patients received a phone call as a reminder to attend follow-up visits. Patients were followed every 2-4 weeks based on physician judgment and pain severity.

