## **Data collection and outcome measures**

The primary outcome of this study was the percentage of patients defined as “pain responders” by either 30% reduction in pain intensity rating or pain intensity less than 4 at the third follow-up visit (FU3). Secondary outcomes included pain interference, other symptom scores, side effects, and analgesic prescribing and consumption.

Data were collected at baseline and at three follow-up times (FU1, FU2, FU3). Patients' baseline demographic data (age, gender, marital status, and education) and clinical characteristics (Cancer status, stage, and sites of involvement) were recorded. Pain severity, performance status, pain interference, other symptoms, side effects, pharmacological treatments and dosage, and patient satisfaction were recorded at every visit. We retrospectively reviewed palliative care medical records for additional data related to pain intensity, performance status, opioid

consumption, date of first palliative care visit, and dates of death, if applicable. Data were collected by research assistants, nurses, and physicians and entered into Case Report Forms.

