### **Statistical analysis Plan**

Analyses were performed using SPSS statistical package 21.0 (SPSS, Inc., Chicago, IL). Categorical data are reported as numbers and percentages, and continuous data are reported as median (IQR). Repeated measures designs used Friedman tests for continuous data and Cochran's Q for dichotomous data, with post-hoc comparisons at each time point using the Wilcoxon matched-pairs signed rank test for continuous variables, McNemar tests for dichotomous variables, and the Marginal Homogeneity test for a categorical variable with 3 or more values. Comparison of continuous variables between two independent populations was assessed using the Mann-Whitney test. Comparison between more than two independent populations was assessed using the Kruskal-Wallis test, with post-hoc Dunn's Bonferroni tests between groups. Variables with p-value<0.1 in the bivariable analyses were considered for entry in subsequent multivariable analyses. A significance level of 0.02 was chosen to account for repeated comparisons across 3 time points.

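### Does reading the primary outcome at the third follow-up visit, with no fixed day, leave the responder percentage undefined in time?

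*Combined protocol and SAP*

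**What the plan says.** In the section on data collection and outcome measures, a responder is defined "by either 30% reduction in pain intensity rating or pain intensity less than 4 at the third follow-up visit (FU3"). The same section describes the schedule by order alone: "Data were collected at baseline and at three follow-up times (FU1, FU2, FU3"). The spacing comes from the Study Protocol section: "Patients were followed every 2-4 weeks based on physician judgment and pain severity". No calendar day, week or window is attached to any visit.

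The content of each assessment is listed as follows: "Pain severity, performance status, pain interference, other symptoms, side effects, pharmacological treatments and dosage, and patient satisfaction were recorded at every visit". Two dates are named, "date of first palliative care visit, and dates of death, if applicable", both in the sentence about reviewing palliative care records.

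The Statistical analysis Plan treats the visits as ordered repeated measures, "with post-hoc comparisons at each time point using the Wilcoxon matched-pairs signed rank test for continuous variables". For description it says that "continuous data are reported as median (IQR"). Time from baseline to FU3 is not singled out as an item to report.

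**The concern.** A responder percentage in a single group usually needs a time frame to be interpreted. Here the interval between visits is flexible, and it depends partly on pain severity, the variable that defines response. Two patients can both be at FU3 with one having had about 6 weeks of care and the other about 12. The words used for the visits, times in one section and time points in another, could lead a reader to assume a common day.

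If that reading took hold, the headline percentage would be quoted as a rate at a fixed time that the schedule does not deliver. The period in which a patient could die before the primary assessment would also differ between patients, with nothing in the plan to show by how much.

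**Working it through.** **Inputs.** The shortest and longest intervals are 2 and 4 weeks, that is 14 and 28 days (Study Protocol). The primary assessment is the third of three follow-up visits (Data collection and outcome measures). One assumption is added: the same interval applies from baseline to FU1. The plan states no day for FU3, so there is no figure of its own to reproduce.

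**Nominal timing.** Visit *k* falls between *k* × 14 and *k* × 28 days.

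| Visit | Earliest | Latest | Spread |
|---|---|---|---|
| FU1 | 1 × 14 = 14 | 1 × 28 = 28 | 14 days |
| FU2 | 2 × 14 = 28 | 2 × 28 = 56 | 28 days |
| FU3 | 3 × 14 = 42 | 3 × 28 = 84 | 42 days |

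For FU3 the ratio of latest to earliest is 84 / 42 = 2. FU2 and FU3 overlap on days 42 to 56, so one patient's FU2 can come later than another's FU3. Even spacing of 21 days puts FU3 at day 63. The two extremes need all three intervals at the same limit, and late or missed visits could widen the range. Without the assumption about the first interval, only the gap from FU1 to FU3 is fixed, at 28 to 56 days.

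**Is the definition missing?** No. The outcome is set by "pain intensity less than 4 at the third follow-up visit (FU3"). *Third* is an ordinal, so the endpoint is a visit-order endpoint as written. A sentence giving days 42 to 84 would only multiply the stated interval by three.

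**Do the tests depend on elapsed time?** No. The Friedman, Cochran's Q, Wilcoxon matched-pairs and McNemar tests compare a patient's value at one ordered visit with the same patient's value at another. Days since baseline do not enter. The FU3 percentage is a count over patients at that visit, and it does not use days either.

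**Were visit dates left uncollected?** The documents do not show this. The two named dates belong to a retrospective look through a different set of records. The prospective list gives the clinical content of each visit, and its silence on the date does not mean that the case report forms carried none.

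**Would a fixed-day analysis do better?** Take day 56 as an illustration and use the nearest visit. With even spacing of 14 days the nearest is FU3 (day 42, 14 days away). With 21 days it is FU3 (day 63, 7 days away). With 28 days it is FU2 (day 56, 0 days away). The result would mix patients after two reassessments with patients after three, which is a different quantity. Day 56 has no basis in the documents. Deaths would also need an extra rule: a patient seen on day 42 who dies on day 50 has a visit within 14 days of day 56 and has also died before it.

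**The case for a change.** The strongest case for acting is that this is the primary endpoint and the remedy is cheap: one descriptive row of days to FU3. Because spacing depends on pain severity, time to FU3 may be related to response, and a reader cannot check this without the days. The period at risk of death before FU3 also varies, nominally from 42 to 84 days.

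Part of this stands. The plan does not name the time actually taken to reach FU3, and a reader of the results would find it useful. But the nominal range is already available from the two sections read together, and the observed distribution is a result, which a plan cannot contain. The general median and IQR rule covers it, and most analysts holding the dates would report it without being told.

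A split of days by responder status would be harder to defend. Pain severity influences the spacing, so a difference could reflect pain driving the timing, yet be read as timing driving response. How many patients reached FU3, and how many died first, is a question of denominators and missing data, and it does not depend on whether FU3 has a fixed day.

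**Conclusion.** The arithmetic is right: FU3 falls nominally on day 42 to day 84, given a 2-4 week interval throughout, including baseline to FU1. No change to the plan follows. In an observational study of standard care, response after three follow-up visits is a legitimate quantity. It is stated as such, and following the plan exactly yields it.

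The wording about times and time points is ordinary labelling of ordered visits, and nowhere does the plan claim a rate at a fixed week. Any effect of timing on the percentage cannot be sized from the documents and may be nil.

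What remains is a reporting courtesy. If visit dates were recorded, median (IQR) days from baseline to FU3 can sit beside the percentage. The sections are written in the past tense, so this should be labelled post hoc if the data have already been analysed. It would alter no test, estimate or conclusion.

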## **Data collection and outcome measures**

The primary outcome of this study was the percentage of patients defined as “pain responders” by either 30% reduction in pain intensity rating or pain intensity less than 4 at the third follow-up visit (FU3). Secondary outcomes included pain interference, other symptom scores, side effects, and analgesic prescribing and consumption.

Data were collected at baseline and at three follow-up times (FU1, FU2, FU3). Patients' baseline demographic data (age, gender, marital status, and education) and clinical characteristics (Cancer status, stage, and sites of involvement) were recorded. Pain severity, performance status, pain interference, other symptoms, side effects, pharmacological treatments and dosage, and patient satisfaction were recorded at every visit. We retrospectively reviewed palliative care medical records for additional data related to pain intensity, performance status, opioid

consumption, date of first palliative care visit, and dates of death, if applicable. Data were collected by research assistants, nurses, and physicians and entered into Case Report Forms.

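### The planned within-patient tests show only net change in side effects between visits; counts of onset and resolution should be added

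*Combined protocol and SAP*

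**What the plan says.** The section on data collection and outcome measures names the secondary outcomes: "Secondary outcomes included pain interference, other symptom scores, side effects, and analgesic prescribing and consumption". Side effects are the only harm outcome in that list. Data are collected at baseline and at three follow-ups, and the same section states: "Pain severity, performance status, pain interference, other symptoms, side effects, pharmacological treatments and dosage, and patient satisfaction were recorded at every visit". Each patient's baseline side-effect status should therefore be on file.

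The statistical analysis plan names no outcome. It assigns methods by type of variable:
- Description: "Categorical data are reported as numbers and percentages".
- Comparison across visits: "Repeated measures designs used Friedman tests for continuous data and Cochran's Q for dichotomous data".
- Post-hoc paired comparison: the Wilcoxon signed-rank test for continuous variables, then "McNemar tests for dichotomous variables, and the Marginal Homogeneity test for a categorical variable with 3 or more values".
- Threshold: "A significance level of 0.02 was chosen to account for repeated comparisons across 3 time points".

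Neither section says how side effects are scored (yes/no, categories or a scale). Neither defines new onset, an at-risk denominator, cumulative incidence or a severity grade.

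**The concern.** For a harm outcome, a reader wants to know how many patients acquired a side effect during follow-up. None of the listed tests answers that. McNemar's test sets patients who gain an effect against those who lose one. Cochran's Q asks whether the visit proportions are equal. Marginal homogeneity, Friedman and Wilcoxon tests likewise offset worsening in some patients against improvement in others. The mechanism is therefore the same whichever way side effects were scored.

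At stake is what the study can say about harm. A non-significant test invites the summary that side effects did not increase. That may be true of the group total while many individual patients have a new complaint. Percentages by visit do not reveal the turnover either.

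**Working it through.** **The plan's own figure.** The only design figure relevant here is the 0.02 threshold. The overall level it protects is not stated. If 0.05 is assumed, 0.05/3 = 0.0167, which rounds to 0.02. The point does not rest on this, because in the balanced case below p = 1 at any threshold.

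**Inputs.** From the documents: four assessment times, the list of tests, and 0.02 (taken as two-sided). Assumed, because the documents give none of them: 100 patients with paired data, a yes/no side effect, and the baseline, resolution and onset figures shown.

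**One follow-up against baseline.** Exact McNemar uses only the patients who change. With g gaining and l losing the effect, p = 2 × P(X ≤ min(g, l)), where X is binomial with g + l trials and probability 0.5, capped at 1. Onset is g divided by the number free at baseline.

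| Affected at baseline | Lost (l) | Gained (g) | Affected at follow-up | Onset among those free | p |
|---|---|---|---|---|---|
| 40 | 20 | 20 | 40 − 20 + 20 = 40 | 20/60 = 33% | 1.00 |
| 40 | 20 | 30 | 40 − 20 + 30 = 50 | 30/60 = 50% | 2 × 0.101 = 0.20 |
| 20 | 10 | 16 | 20 − 10 + 16 = 26 | 16/80 = 20% | 0.33 |
| 20 | 10 | 27 | 20 − 10 + 27 = 37 | 27/80 = 34% | 0.008 |
| 0 | 0 | 10 | 10 | 10/100 = 10% | 2 × 0.5^10 = 0.002 |

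In the first row the planned test reports no change at all. The same data give an onset of 33%, with a Clopper-Pearson 95% interval of 22% to 47%.

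**How many new cases can stay non-significant at 0.02.** The largest g is 6 if none resolve, 16 if 5 resolve, 24 if 10 resolve and 38 if 20 resolve.

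**All four visits.** Cochran's Q was simulated 2,000 times per setting at 0.02, with constant onset and resolution probabilities per visit.
- 40% affected at baseline, onset 1/3, resolution 1/2: prevalence stays level, because (1/3)/(1/3 + 1/2) = 0.40. Q rejects in 2.2% of runs with 100 patients and 2.6% with 200, about its nominal rate. Yet 1 − (2/3)^3 = 70% of those free at baseline have the effect at some follow-up.
- 10% affected at baseline, same rates: expected prevalence at FU1 is 0.10 × 1/2 + 0.90 × 1/3 = 35%. Q rejects in at least 99.9% of runs at either sample size.

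The two settings differ only in baseline prevalence, so masking is strong in one and practically absent in the other.

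**The case against.** Five objections deserve weight.

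1. *The documents never say that side effects are dichotomous.* Correct. To say that they are tested as net prevalence is an inference from general methods. Net change is what can be said, and it holds for every listed test.
2. *Baseline may hold few side effects.* A reader might infer that baseline already contains side effects of earlier analgesics and symptoms of the cancer. For patients newly referred with cancer pain this is plausible, but no prior analgesic use or baseline frequency is reported. Other symptoms are also listed as an item separate from side effects, which suggests an intent to keep the two apart. If baseline prevalence is low, the planned tests detect onset well, as the calculations show.
3. *Visit prevalence is a legitimate measure.* It describes the burden carried by a clinic's patients. Onset counts complement it and do not show it to be the wrong measure.
4. *Onset is not harm from treatment.* The study observes a single group under usual clinic care. A new complaint may come from disease progression or other treatment, and an onset count cannot tell these apart.
5. *The misreading is hypothetical.* Nothing in the plan says that a non-significant test will be reported as absence of harm, and percentages are promised alongside the tests. That is fair, but those percentages are visit totals and still do not show who is newly affected.

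What remains is the gap itself: the plan states no quantity that separates onset from resolution.

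**Conclusion.** The point holds as a gap in reporting for one secondary outcome. The plan's within-patient tests assess net change, and nothing in it counts onset, so a non-significant test does not exclude frequent new side effects.

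The size of the problem is unknown. Under assumed figures it runs from complete masking (33% onset, p = 1) to none (10% onset, p = 0.002), driven by baseline prevalence and resolution. The documents do not support the stronger reading that the plan will hide treatment harm: they give no baseline rate, and the design cannot attribute onset to treatment. The primary outcome is unaffected. This is a cheap improvement that adds to the planned tests and does not replace them.

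**What to change.** Keep the prevalence-by-visit table and the planned tests. In the statistical analysis plan, state how side effects were scored, and add for each one:

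- (a) among patients free of it at baseline who have any follow-up visit, the number and percentage reporting it at any of FU1 to FU3 and at each visit, with a 95% confidence interval;
- (b) counts of new, resolved and persistent cases at each visit, with the number of patients assessed.

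Add worsening from baseline only if side effects were graded, since it cannot be derived from present/absent records. Using everyone with any follow-up also keeps patients whom a standard Cochran's Q drops for a missed visit. Describe the result as onset during follow-up, not as an effect of treatment. State that a non-significant Cochran's Q or McNemar test will not be read as absence of new side effects.

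The cost is a few sentences and one cross-tabulation per side effect, from data already collected. The drawback for the authors is that the onset figure may look less favourable than net change.

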### **Statistical analysis Plan**

Analyses were performed using SPSS statistical package 21.0 (SPSS, Inc., Chicago, IL). Categorical data are reported as numbers and percentages, and continuous data are reported as median (IQR). Repeated measures designs used Friedman tests for continuous data and Cochran's Q for dichotomous data, with post-hoc comparisons at each time point using the Wilcoxon matched-pairs signed rank test for continuous variables, McNemar tests for dichotomous variables, and the Marginal Homogeneity test for a categorical variable with 3 or more values. Comparison of continuous variables between two independent populations was assessed using the Mann-Whitney test. Comparison between more than two independent populations was assessed using the Kruskal-Wallis test, with post-hoc Dunn's Bonferroni tests between groups. Variables with p-value<0.1 in the bivariable analyses were considered for entry in subsequent multivariable analyses. A significance level of 0.02 was chosen to account for repeated comparisons across 3 time points.
